1.17. Bronchoscopy

Bronchoscopies will be performed in either the ICRF at Hammersmith Hospital, or the Endoscopy suite at St Mary's or Hammersmith Hospitals, in accordance with BTS guidelines. During the confinement period, private transport from the confinement facility to the Endoscopy suite will be mandatory. Subjects will be instructed to wear facemasks during this visit, and staff will use appropriate personal protective equipment (PPE). Bronchoscopies will be performed at baseline (Day -14), during the in-patient stay (between Day 7-9), and at Day 28 and 180 follow-ups.

- Subjects will sign a consent form prior to being screened for the study and will **sign a separate consent form for each bronchoscopy**. The procedure will be explained during the assessment stage and **subjects will be given written information specifically regarding bronchoscopies in addition to the Participant Information Sheet**
- Subjects will fast for four hours prior to the procedure.

- Resuscitation equipment (for intubation, ECG monitoring and defibrillation) and necessary drugs (salbutamol, theophylline, adrenaline, hydrocortisone) will be available in the bronchoscopy room.
- Premedication will be given including:
 - Sedation – Midazolam (2-10mg) and/or Fentanyl (25-100 μ g) as necessary.
 - Topical anaesthesia – Lignocaine solution (1-4%). The total dose will not exceed 400mg.
- Supplemental oxygen at a rate of 2Lmin⁻¹ is given via a nasal cannula and adjusted as appropriate, and oxygen saturations and heart rate are monitored with a pulse oximeter continuously. Intravenous access will be mandatory in all cases
- The subject will be monitored during the bronchoscopy by a separate nurse and a second suitably qualified physician will be present to act as an advocate
- The following samples are collected in this order: (i) Bronchosorption using Synthetic Absorptive Matrix (SAM) (ii) Bronchial Brushings (iii) Bronchial Biopsy (iv) Bronchoalveolar lavage (BAL)
- All adverse events – pain, bleeding, hypoxia etc. will be recorded and reported according to Section 8 of this protocol.
- Subjects will be observed for a minimum of 2 hours and will remain nil by mouth after the procedure recovered.
- Transportation will be arranged as subjects should not drive on the day of the procedure.
- All subjects will have a contact telephone number on discharge to ring in case of any issues.

1.17.1. Bronchosorption:

Bronchosorption™ FX·i is a non-sterile, single-use device consisting of a synthetic absorptive matrix (SAM™) strip enclosed within a catheter for bronchial sampling. Bronchosorption™ FX·i is designed to operate through a flexible video bronchoscope with a maximum working length of 815mm. The SAM™ strip is 1.0mm wide, designed to work with a minimum instrument channel diameter of 2.0mm.' Hunt Developments UK (Ltd).

- The device will be passed down the bronchoscope.
- The probe will be deployed for up to 120 seconds in segmental and larger bronchi to allow the SAM to absorb local epithelial lining fluid (ELF).
- The probe will then be re-sheathed and removed via the operating port of the bronchoscope.
- This will be repeated up to 4 times with a new device.

The SAM will be transferred to polypropylene tubes for transport on ice to the laboratory and stored at -80°C until analysis.

1.17.2. Bronchial Biopsies:

Up to eight bronchial biopsies will be taken from the segmental and sub-segmental bronchi of the right lower and middle lobe (RLL, ML). This is performed using Keymed 2mm biopsy channel cupped and fenestrated biopsy forceps [FB-19C-1 (1111065)]; four biopsies will be placed in 4% paraformaldehyde and stored in paraffin blocks and two placed immediately into RNAlater® (Qiagen) stabilisation solution and refrigerated for 24 hours prior to freezing at -80°C.

1.17.3. Bronchial Brushings:

Four bronchial brushings will be taken from the left lower lobe (LLL) sub-segmental bronchi with a standard cytology brush. The brush is washed in a tube containing RNA Cell Protect® (Qiagen) to preserve cells prior to freezing at -80°C. A new brush is used each time the brushes are washed and discarded.

1.17.4. Bronchoalveolar Lavage (BAL):

- BAL is performed by instillation of sterile physiological (0.9%) saline at room temperature into the left upper lobe (LUL) bronchus in 30-60ml aliquots to a total of 180-240ml.
- Aiming for 80% volume recovery and aspirating after each instillation.
- The BAL fluid is collected into a plastic chamber and transferred to polypropylene tubes for transport on ice to the laboratory.
- BAL processing - Keep BAL collected at bronchoscopy on ice at all times.

1.18. Blood sampling

Screening visit blood will be taken for full blood count, renal function, liver function tests, glucose, clotting, and CRP, immunoglobulins, lymphocyte subsets, and HIV, HBV and HCV serology. These will be processed in the Haematology, Chemical Pathology, Immunology and Virology Laboratories of Imperial College Healthcare NHS Trust. Serology will be performed at screening and Day 28 by IgG microneutralisation and ELISA assays.

The total amount of blood taken at screening would amount to 42.5mL. Blood for peripheral blood mononuclear cells (PBMCs) will also be taken at Day -14, 0, 3, 7, 10, 14, 28 and 180. On these occasions, 20-60mls of blood will be taken (see Table 1). In addition, blood for gene expression profiling, serum and plasma will be taken. Blood for gene expression profiling will be taken once or twice day. A maximum of 80 mls of blood will be taken on any single day for a total of 455 mls over the 28 day challenge period (see Table 1).

DNA processing will be taken from the residual or additional blood samples provided by the subjects.

1.19. Physical examination

Physical examination, including ENT, respiratory and cardiac assessment will be performed by the study doctor at screening and Days -14, 0 (prior to inoculation), discharge, and 14 and 28 days post inoculation.

1.20. Chest X-Ray

All patients eligible to participate in the study will have a single chest X-Ray performed prior to their first bronchoscopy. This is as per our local research bronchoscopy guidelines. The radiation dose associated with a single chest X-Ray is minimal and the risk of adverse effects is negligible.

1.21. Lung Function Tests

Predicted Values for Lung Function Measurements: the predicted or reference values for lung function measurements are those recommended by the Report Working Party for the European Community for Coal and Steel. Also incorporated are the recommendations of the British Thoracic Society and the Association of Respiratory Technicians and Physiologists.

Measuring FEV₁ and FVC by Spirometry

Performing the measurement:

- Posture must be consistent during a study, either standing or sitting, with no breathing limitation
- The subject should breathe in fully. A good tight seal by the lips round the mouthpiece is essential. The subject should then exhale forcibly into the spirometer, blowing as hard as possible and continue to residual volume
- The best value of 3 attempts will be recorded.

At the screening visit and at other visits as described in Table 1, measurements of FEV1 and FVC will be made as outlined above.

1.22. Clinical symptom scores

A self-completed diary card of upper respiratory tract clinical symptoms will be made at baseline 14 days prior to inoculation (prior to nasal washing and/or bronchoscopy), on Day 0, and daily for 14 days after inoculation.

Additionally, the symptom diary will be completed daily for 7 days after the 1st bronchoscopy (i.e. Day -14 to Day -7). This is to allow the effect of bronchoscopy on symptoms to be measured and adjusted.

Individual symptom scores will be accumulated over the ten-day period after inoculation and the baseline recording (including any effect measured from the 1st bronchoscopy where appropriate) subtracted from the post inoculation recordings. Thus, for a patient who has a score of zero on day 0 prior to inoculation, the maximum cumulative score for the following 10 days is 240.

Upper Respiratory Tract Symptoms

A total 'upper respiratory clinical symptom score' will be derived using a four-point scale (0-3 for absent, mild, moderate and severe) for each of the following eight respiratory symptoms: sneezing, nasal discharge, nasal obstruction, and sore throat according to established methods, giving a maximum clinical severity score of 12. This is an established method for studies of common cold illnesses.⁴⁴ Symptoms will be recorded at the same time of day and before any procedures such as bronchoscopy or nasal lavage are performed.

An example is shown below:

Symptom	Day 1	Day 2	Day 3	Day 4	Day 5	Day 6	Day 7
Sneezing							
Runny nose							
Stuffy/blocked nose							
Sore throat							
Total Upper Respiratory score:							

0 = absent, 1 = mild, 2 = moderate, 3 = severe

Definition of a clinical cold

A clinical cold is diagnosed if **two or more** of the following are present:

- A cumulative clinical symptom score of 14 or greater over a 7 day period
- Nasal discharge is present on three or more days over the ten-day period post viral inoculation
- A subjective impression of a cold. This latter criterion is used because there are a few subjects who have had a very strong subjective impression of a clinical cold but the cumulative clinical score does not reach the arbitrary cut-off level

Lower Respiratory Tract and Systemic Symptoms

An extended symptom diary (Appendix 1) based on influenza challenge scoring systems will be used to investigate the usefulness of recording lower respiratory and systemic symptoms in RSV challenge of older adults.

ADVERSE EVENTS

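### Section 1.22 mixes a four-item and an eight-item version of the upper respiratory symptom score, and does not say which one the clinical-cold cut-off of 14 uses

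*Combined protocol and SAP*

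**What the plan says.** All the relevant text is in section 1.22 (Clinical symptom scores) of the combined protocol and SAP.

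- Accumulation: "Individual symptom scores will be accumulated over the ten-day period after inoculation", with the baseline recording subtracted. For a participant with a pre-inoculation score of zero, "the maximum cumulative score for the following 10 days is 240".
- Items: each symptom is rated 0 to 3. The score is to be built from "eight respiratory symptoms: sneezing, nasal discharge, nasal obstruction, and sore throat according to established methods, giving a maximum clinical severity score of 12". The example diary that follows has four symptom rows, matching the four named symptoms, and a row for the upper respiratory total.
- Clinical cold: two of three criteria are needed. One is "A cumulative clinical symptom score of 14 or greater over a 7 day period". The others are nasal discharge on at least three of the ten days, and the participant's own impression of having a cold.
- Lower respiratory and systemic symptoms go into a separate extended diary (Appendix 1), which is being tried out for its usefulness. Nothing says that its items enter the score described above.

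The score is used in two other places. Section 1.6 (Pilot safety study) lists symptom scores among the items reviewed after Group 4 and again at the last interim analysis after Group 6. The statistics section plans within-participant comparisons of symptom scores between baseline and infection, and correlations involving illness severity.

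**The concern.** The item count and one maximum belong to an eight-item score; the named symptoms, the other maximum and the diary belong to a four-item score. An analyst following section 1.22 cannot tell which total to compute. The cold criterion inherits the doubt, because a fixed threshold of 14 is easier to reach when more items are summed and the text does not say which list it was set on.

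What is at stake is the description of tolerability and symptomatic illness. Safety and tolerability form the primary objective (section 1.3). Section 1.24.1 says that ordinary cold symptoms are not treated as adverse events unless the study doctor decides otherwise. By inference, much of the quantitative information on how well challenge was tolerated will sit in the symptom score. With at most 42 participants, even a few reclassified colds would visibly move a proportion. If the list is chosen after scores have been seen, the case definition can follow the results.

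**Working it through.** **Inputs, all from section 1.22.** Item range 0 to 3; four symptoms named, eight stated; accumulation over 10 days; stated maxima 12 and 240; cut-off 14 over 7 days; cold = two of three criteria. The text does not label the 12 as a daily figure; that follows from four items at 3 points in one daily recording.

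**Formula.** Maximum = items × 3 × days, with baseline zero.

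**Reproducing the stated figures.**

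| | Four items | Eight items | Stated |
|---|---|---|---|
| Per day | 4 × 3 = 12 | 8 × 3 = 24 | 12 |
| 10 days | 12 × 10 = 120 | 24 × 10 = 240 | 240 |
| 7 days | 12 × 7 = 84 | 24 × 7 = 168 | not given |

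Four items reproduce the 12 but not the 240. Eight reproduce the 240 but not the 12. The gap is a factor of 2.

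**Could another window rescue 240 on four items?** Days 0 to 10 (11 days): 12 × 11 = 132. Fourteen days: 12 × 14 = 168. Reaching 240 at 12 a day needs 240 / 12 = 20 days, or an item maximum of 240 / (10 × 4) = 6. Neither fits the text.

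**Position of the cut-off.** Four items: 14 / 84 = 16.7% of the 7-day maximum, or 14 / (4 × 7) = 0.50 points per item per day. Eight items: 14 / 168 = 8.3%, or 14 / (8 × 7) = 0.25. The cut-off can be reached on either list.

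**When does the diagnosis change?** Count how many of the two other criteria (discharge, subjective cold) a participant meets.

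- Neither: not a cold on either list, since the score alone is one criterion.
- Both: a cold on either list, whatever the score.
- Exactly one: the score decides, so the diagnosis changes if the total reaches 14 on one list only.

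**Two illustrations**, assuming baseline zero and that an eight-item list would contain the four named symptoms.

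- Mild scores (1) on all eight items for two days: 8 × 1 × 2 = 16 against 4 × 1 × 2 = 8. Discharge lasts only two days, so that criterion fails. If the participant also reports a subjective cold, this is a cold on eight items and not on four. Without that report it is not a cold on either list.
- Mild scores on all eight items for three days: 8 × 1 × 3 = 24 against 4 × 1 × 3 = 12. Discharge on three days meets its criterion. If the participant does not report a subjective cold, this is again a cold on eight items only.

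**The case against.** The strongest reply is that the parts of section 1.22 that would actually be used agree with each other. The named symptoms, the maximum of 12 and the diary rows all point to four items. The outliers are one word and one illustrative sentence, and nothing in the analysis uses 240 or expresses a score as a fraction of its maximum. The section itself calls the cut-off arbitrary. Within-participant comparisons can be made on whichever items are collected.

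Much of this stands. Four items is the more natural reading, and the percentages above describe how the stringency of the cut-off shifts; they do not show that 14 is wrong. But the text does not settle the matter, and an unnamed list behind a fixed threshold is a genuine gap in a case definition.

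A reader might infer more than the documents support:

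- *That safety decisions turn on the score.* They do not. The pausing criteria in section 1.6 are death, serious adverse events, unexpectedly severe disease and severe unexpected events. The step after Group 4 depends on at least four PCR-defined infections and no pausing trigger. The suspension and referral rules in section 1.24.1 do not use the score either.
- *That the 7-day and 10-day windows conflict.* One belongs to a diagnostic criterion and the other to a severity total; they need not match.
- *That comparison with the roughly 66% symptomatic rate in earlier challenges (section 1.1) is undermined.* The protocol does not say that this score or cold definition produced that figure, and plans no such comparison.
- *That the missing four items are already in the extended diary.* Appendix 1 is not among the documents supplied, so this cannot be checked.

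**Conclusion.** The contradiction is certain and rests on arithmetic alone: the two stated maxima imply different item counts, and the 10-day maximum is either 120 or 240. The cut-off of 14 is tied to neither list, and its position relative to the 7-day maximum differs two-fold (16.7% against 8.3%).

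The consequence is real but limited. Clinical-cold status changes only for participants who meet exactly one of the other two criteria and whose total crosses 14 on one list only. The documents give no basis for estimating how many that would be. The sample size and all pausing and go/no-go rules are unaffected. What is affected is the meaning of the symptom scores seen in the pilot safety and interim reviews, the planned symptom-score analyses, and any reported rate of clinical colds. It would be too strong to say that the score has no usable scale: the four-item version is complete as written, but the section does not commit to it.

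The illustrations assume baseline zero and an eight-item list that includes the four named symptoms.

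**What to change.** Before any symptom scores are analysed, reconcile section 1.22 to one item list.

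- If the four named symptoms are intended, as the diary suggests: change eight to four, and 240 to 120.
- If eight are intended: name all eight, add the missing four to the diary, and change 12 to 24.
- In either case, state which item list the cut-off of 14 was set on, and compute that criterion on that list only.

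On the four-item reading the cost is a wording amendment, with no change to data collection. On the eight-item reading the diary card changes too. Participants who have already completed a four-row diary could then be scored on eight items only if the other four were recorded elsewhere, which the sponsor would need to check against Appendix 1.

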1.23. Definitions

Adverse Event (AE): any untoward medical occurrence in a patient or clinical study subject.

Serious Adverse Event (SAE): any untoward and unexpected medical occurrence or effect that:

- **results in death**
- **Is life-threatening** – refers to an event in which the subject was at risk of death at the time of the event; it does not refer to an event which hypothetically might have caused death if it were more severe
- **requires hospitalisation**
- **results in persistent or significant disability or incapacity**
- **is a congenital anomaly or birth defect**

Medical judgement should be exercised in deciding whether an AE is serious in other situations. Important AEs that are not immediately life-threatening or do not result in death or hospitalisation but may jeopardise the subject or may require intervention to prevent one of the other outcomes listed in the definition above, should also be considered serious.

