1.2. Research Hypotheses

1. RSV challenge remains safe and tolerable in older adults
2. Humoral and cell mediated immune responses in the airway represent direct correlates of protection against RSV
3. Aging leads to impaired RSV-specific cell mediated immunity and, to a lesser extent, humoral immunity
4. Impaired antigen-specific adaptive immunity in elderly adults leads to increased susceptibility to symptomatic RSV disease

STUDY OBJECTIVES

1.3. Primary Objective:

- Safety and tolerability of experimental challenge with RSV Memphis 37

1.4. Secondary Objective:

- To measure RSV-specific antibody, B cell and T cells in the blood and airway before, during and after infection with RSV in an elderly cohort

1.5. Exploratory Objectives:

- To compare the quantitative and qualitative features of adaptive immune responses against RSV in the elderly with young adults

STUDY IMPLEMENTATION

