1.6. Pilot safety study

A pilot safety study will be performed to determine safety and tolerability of deliberate RSV infection in older adults.

This will be performed according to the sub-protocol “Accelerating RSV vaccine development in elderly (60-75 year old) adults by extending the controlled human infection model: a pilot safety study” (see Appendix 1-3). To ensure that the clinical team can closely monitor participant safety and to remain within the capacity of the quarantine unit, study participants will be divided into groups. The first 10 participants will be challenged in sequential cohorts as follows, with a younger sentinel group followed by older groups with pausing rules to ensure RSV disease remains within an expected mild-moderate range. Safety will be assessed at the end of quarantine (day 10 post-inoculation) for each group at which time, if no pausing criteria are met, the next group will be allowed to proceed as follows:

1. Group 1 (n=2, aged 60-67)
2. Group 2 (n=3, aged 60-67)
3. Group 3 (n=2, aged 68-75)
4. Group 4 (n=3, aged 68-75)

If any of the following pausing criteria are met, further viral challenges will be suspended until the Safety Monitoring Committee has met and approved re-commencement.

1. Occurrence of any death occurring after RSV challenge
2. Occurrence of any SAE
3. Occurrence of any unexpectedly severe disease as described in Section 1.20.1
4. Occurrence of any severe (non-serious) unexpected AE considered at least possibly related to the viral challenge

At the end of each quarantine period, the next group will be scheduled for quarantine if none of the following pausing rules is met.

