At the end of the quarantine period (Day 10 post-inoculation) of Group 4, a safety review of the first 10 participants will be carried out to assess the extent of expected and unexpected adverse events, viral shedding and symptom scores. If at least 4 subjects are infected (as defined by PCR detection of virus on at least 2 consecutive days) and none of the infected subjects exhibit any safety concerns (that would trigger a pausing rule), the investigators will discuss the feasibility of intensifying the sampling regime, for example with the addition of bronchoscopy. If less than 4 subjects are infected in the first 10 challenge participants, the pilot study will continue with no intensification of sampling (i.e. no bronchoscopy). A further interim analysis will be performed after the Day 28 post-infection time-point of the first 10 participants. The remaining participants will be challenged in groups as follows:

5. Group 5 (n=5, aged 60-67)
6. Group 6 (n=5, aged 68-75)

The last interim analysis will be performed after the Day 28 post-infection time-point of Group 6 for assessment of attack rate, symptom scores and viral load. A minimum of 4 infected subjects without safety concerns in the first cohort supports a probability of at least 80% for the absence of safety concerns in the next 5 infected subjects from the second cohort. Prior to the first cohort, we assume a probability of 50% or more for the absence of safety concerns in the first Group of 4 or 5 infected subjects, based on our experience in younger subjects. The calculations assume, prior to the first cohort, a 95% credible interval for the probability of safety concerns covering a range between 0% and 97% and centred around 27.5%. Prior to the second cohort, assuming at least 4 infected subjects and no safety concern, the 95% credible interval would cover a range between 0% and 34% and centred around 5.5%. The probability of an absence of safety concerns in a Group 4 or 5 subjects is calculated using a beta-binomial distribution with parameters 0.275 and 0.725 prior to the first cohort, and 0.275 and 4.725 prior to the second cohort. The probability of no event in 4 or 5 subjects from those distributions are equal to ~50% and ~80% respectively prior to the first and prior to the second cohort.

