1.24. Expected adverse events

1.24.1. Potential adverse events related to RSV infection

We would expect subjects to experience typical symptoms of a common cold (including, but not limited to: fever, headache, malaise, rhinorrhoea, nasal congestion, sneezing, sore throat, and cough). These would not be deemed adverse events, unless in the opinion of the study doctor. However, fever greater than 38°C for more than three consecutive days or withdrawal from the study due to intolerable symptoms in more than two subjects in any arm will lead to a suspension of the study. The safety monitoring committee will be convened to determine any systematic cause for unexpectedly severe symptoms.

Any illness resulting in

- **Sustained elevated heart rate >120bpm AND**
- **Sustained low blood pressure SBP<100**
- **Sustained elevated respiratory rate >30/min AND**
- **Sustained low blood oxygen SaO₂<94%**
- **Evidence of pneumonia on clinical examination**

will lead to referral for assessment in Accident and Emergency. Hospitalisation of any subject will lead to immediate suspension of the trial. The safety monitoring committee will be convened to assess the clinical evidence to determine whether the study may proceed.

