1.24.2. Potential adverse events of bronchoscopy

Bronchoscopy is a safe procedure, with serious complications occurring in less than 1 in 1000 procedures. It is frequently performed on patients with lung diseases such as asthma, and even in critically-ill and frail elderly patients. The bronchoscopy may cause cough for a few hours, and there may be some discomfort during the procedure, but this is reduced with local anaesthetic and sedation.. The sedation makes participants drowsy, but this usually wears off after a few hours. Participants should not drink alcohol after receiving sedation. Minor bleeding caused by irritation of the airways from the telescope may occur (less than 1 in 100), but this does not require treatment. Serious bleeding requiring treatment is very rare (less than 1 in 1000). The fluid used to wash the airways (lavage) can cause some irritation, which manifests as a brief fever in 10-30% of cases. This is self-limiting and can be treated with paracetamol. On rare occasions the airways can narrow – if this occurs medication can be given to open the airways. Occasionally after taking the tissue sample (biopsy) people can cough up small amounts of blood but this will stop without further treatment. Very rarely (less than 1 in 1000), the lung can collapse (pneumothorax) after bronchial biopsy; we would arrange for all necessary treatment in the unlikely event should this occur.

Bronchosorption is likely to have less adverse effects than bronchoalveolar lavage, brushing and biopsy (the standard bronchoscopy tools) as it should not cause bleeding, infection or a reactive pyrexia. The only additional adverse event relating specifically to bronchosorption is dislodgement of the SAM from the forceps. If this does occur the SAM can be retrieved using standard endobronchial forceps and snares available routinely in the bronchoscopy suite.

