1.25.2. Serious AEs

An SAE form should be completed and faxed to the Chief Investigator and the Sponsor within 24 hours. The safety monitoring committee (see Section 12) will also be informed and a meeting convened as soon as possible.

All SAEs should be reported to the West London REC 2 Research Ethics Committee where in the opinion of the Chief Investigator, the event was:

- 'related', i.e. resulted from the administration of any of the research procedures; and
- 'unexpected', i.e. an event that is not listed in the protocol as an expected occurrence

Reports of related and unexpected SAEs should be submitted to ethics, the sponsor and the R&D office within 15 days of the Chief Investigator becoming aware of the event, using the NRES SAE form for non-IMP studies.

Contact details for reporting SAEs

[contact]

[contact] for the attention of [name] and/or [name]
[contact]

Please send SAE forms to: Section of Infectious Disease, [name], Imperial College London, Hammersmith Campus, [name]
[contact](Mon to Fri 09.00 – 17.00)

ASSESSMENT AND FOLLOW-UP

Study participants will be seen frequently during the study period, and at least daily for 10 days following infection. They have details to contact the study doctor and research nurses and will be offered daily telephone contact. In this way participants will be assessed regularly by the investigating team and any adverse events detected rapidly; subjects meeting the criteria for a serious adverse event will be offered prompt treatment as appropriate.

Subjects will have completed the study when they have had final convalescence investigations, expected to be 180 days after initial inoculation with the RSV virus. The overall study will be completed when sufficient numbers of subjects have been recruited. The end of the study is defined as the last visit of the last participant.

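### The SAE definition makes unexpectedness a condition of seriousness, so a life-threatening event that the protocol lists as expected is, read literally, not an SAE

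*Combined protocol and SAP*

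**What the plan says.** All references are to the combined protocol and SAP.

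- **Objective.** The primary objective (Section 1.3) is "Safety and tolerability of experimental challenge with RSV Memphis 37". No endpoint or summary measure is attached to it.
- **AE.** Section 1.23 defines an adverse event as "any untoward medical occurrence in a patient or clinical study subject", with no condition on expectedness.
- **SAE.** The same section defines an SAE as "any untoward and unexpected medical occurrence or effect that" results in death, is life-threatening, requires hospitalisation, or meets one of the remaining criteria. A closing paragraph lets medical judgement class other important AEs as serious.
- **Unexpected.** The word is explained only in Section 1.25.2, as a filter for reporting SAEs to the ethics committee: "an event that is not listed in the protocol as an expected occurrence".
- **Listed events.** Section 1.24 is headed as the list of expected adverse events. Section 1.24.2 includes pneumothorax after biopsy and states "Serious bleeding requiring treatment is very rare (less than 1 in 1000" procedures).
- **Use of SAEs.** Section 1.25.2 requires a form within 24 hours and an SMC meeting. Pausing criterion 2 in Section 1.6 is "Occurrence of any SAE". That section also describes a safety concern as something that would trigger a pausing rule.
- **Cold symptoms.** Section 1.24.1 says of typical cold symptoms: "These would not be deemed adverse events, unless in the opinion of the study doctor". The review of the first 10 participants (Section 1.6) is "to assess the extent of expected and unexpected adverse events, viral shedding and symptom scores".

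**The concern.** Seriousness describes the outcome of an event. Expectedness describes whether the event was foreseen. Section 1.23 merges the two, so listing a complication in the protocol removes it from the SAE category however bad its outcome. The 24-hour form, the SMC meeting and the any-SAE pausing criterion all depend on that category. The pausing criterion in turn feeds the safety concerns on which pilot progression rests. In a study whose primary objective is safety, the SAE count should not depend on which complications the protocol happened to list.

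There is a secondary problem: the passages on non-serious events do not agree with each other on whether expected events count as AEs, or on which events reach the SMC.

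**Working it through.** **1. The plan's own safety figures.** Section 1.6 gives about 50% and about 80% for the probability of no safety concern in 4 or 5 infected subjects. With a Beta(a, b) distribution, P(no event in n) is the product of (b + i)/(a + b + i) for i = 0 to n − 1.

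- Beta(0.275, 0.725): 52.9% for n = 4 and 50.0% for n = 5.
- Beta(0.275, 4.725): 83.6% for n = 4 and 81.1% for n = 5.

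The figures reproduce. The arithmetic is not in question; what counts as an event is.

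**2. The definition applied to a listed event.** Take a life-threatening pneumothorax after biopsy, managed without admission.

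| Route | Section | Depends on expectedness? | Caught? |
|---|---|---|---|
| SAE main definition | 1.23 | Yes | No |
| Medical-judgement clause | 1.23 | No, but written for events not immediately life-threatening | Not on its wording |
| 24-hour form and SMC meeting | 1.25.2 | Yes, through the SAE definition | No |
| Pausing criterion 1 (death) | 1.6 | No | Only if fatal |
| Pausing criterion 2 (any SAE) | 1.6 | Yes, through the SAE definition | No |
| Pausing criterion 4 | 1.6 | Yes; also non-serious and related to the challenge | No |
| Hospitalisation of any subject | 1.24.1 | No | Only if admitted |
| Recording of bronchoscopy AEs | 1.17 | No | Recorded as an AE |

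Pausing criterion 3 points to Section 1.20.1, which does not exist. Section 1.20 is the chest X-ray, and the matching text appears to be in Section 1.24.1.

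One result is perverse. A lesser listed event can be judged serious under the clause, while a life-threatening one fails the main definition.

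**3. Internal contradiction.** Section 1.25.2 sends SAEs to ethics only if they are related and unexpected. If every SAE were unexpected by definition, the second condition would remove nothing. Section 1.25.2 therefore assumes that SAEs can be expected, and Section 1.23 says they cannot.

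**4. How often it could matter.** Table 1 gives four bronchoscopies per participant. Section 1.8 allows up to 12 young and 30 older participants, the total including up to 20 from the pilot. That leaves 10 to 30 older participants in the main part, depending on how the pilot is counted.

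- Procedures: 12 × 4 = 48 young; 10 × 4 = 40 to 30 × 4 = 120 older; total 88 to 168.
- Section 1.24.2 puts serious complications below 1 in 1000, so the expected number is below 88/1000 = 0.09 to 168/1000 = 0.17.
- Chance of at least one, if procedures are independent: below 1 − 0.999^88 = 8.4% to 1 − 0.999^168 = 15.5%.

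Only the part of these that is life-threatening, non-fatal and managed without admission falls in the gap. Bronchoscopies added in pilot Groups 5 and 6 are not counted, because their number is not given.

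**5. Leverage on the pilot calculation (hypothetical).** Suppose one of four infected subjects had a serious listed event. Not counting it leaves Beta(0.275, 4.725): mean 5.5%, P(no concern in the next 5) 81%. Counting it gives Beta(1.275, 3.725): mean 1.275/5 = 25.5%, P(no concern in the next 5) 35%. This shows sensitivity only. Section 1.6 treats bronchoscopy as a possible addition after the first 10 participants, so a bronchoscopy complication could not enter this first update.

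**6. Secondary inconsistencies.**

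- Section 1.24.1 takes typical cold symptoms out of the AE category by default and gives no criterion for the doctor's opinion, yet they sit under the expected-AE heading and Section 1.6 reviews expected AEs.
- Section 1.25 has the SMC informed monthly of unexpected AEs only. Section 1.25.1 and Study Management have it discuss all.
- On the rates in Section 1.1 (55% infected, 66% of those symptomatic, ages 18 to 55), 0.55 × 0.66 = 36.3%, or 10.9 of 30 older adults, would have such symptoms. If infection is 40–80% and symptoms 50–90%, assumed for older adults, the range is 6.0 to 21.6 of 30.

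**The case against.** The best defence is that the safeguards overlap. Any death and any hospitalisation are acted on whatever was expected. The judgement clause can class treated bleeding or a treated pneumothorax as serious. All bronchoscopy AEs are recorded (Section 1.17), and the SMC can convene for other safety issues (Section 1.25). The listed complications are rare, and bronchoscopy is not part of the first 10 challenges. The word unexpected in Section 1.23 might also carry its ordinary meaning and not that of Section 1.25.2. Finally, the pilot sub-protocol (Appendix 1-3) is not in the supplied text and may hold further definitions.

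Most of this stands and limits the size of the problem. It does not remove it. The safeguards do not restore the SAE form or the SAE count, and none covers on its wording a life-threatening listed event managed without admission. If the word is not defined by Section 1.25.2, it is undefined where it decides what an SAE is.

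A reader might go further and infer that the primary safety endpoint omits the events the study is meant to measure. The documents do not support that. They state an objective and no endpoint. Cold symptoms are scored in a diary on Day 0 and daily for 14 days (Section 1.22), compared with baseline in the statistics section, and reviewed for safety in Section 1.6. They are missing from AE counts, not from the safety data.

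**Conclusion.** The SAE definition is wrong as written and conflicts with Section 1.25.2. The practical gap is narrow: fewer than 0.09 to 0.17 serious bronchoscopy complications expected in the main study, of which only some would escape every other trigger. This rests on the protocol's rate of below 1 in 1000, four procedures per participant, and the meaning of unexpected given in Section 1.25.2. The pausing criteria are written for the pilot, and Section 1.7 does not say whether they carry over. In the main study the certain loss is therefore the SAE form, the SMC meeting and the SAE count.

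It would be tempting to say that uncounted colds bias the progression decision towards safety. That does not follow: a typical mild cold meets none of the four pausing criteria, whether or not it is called an AE. The figure of about 11 in 30 counts participants whose symptoms appear in the diary and not in the AE listing. It is not a measure of bias. The AE and SMC wording needs reconciling, but it is secondary.

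**What to change.** Delete the words *and unexpected* from the SAE definition in Section 1.23, so that seriousness alone defines an SAE. Keep expectedness only in Section 1.25.2, as the filter for ethics reporting. Pausing criterion 2 then takes in serious events whether or not they are listed; the sponsor and the SMC should confirm that this is what they intend.

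Also reconcile three sets of passages: Section 1.24.1 with Section 1.6 on whether expected cold symptoms are AEs; Section 1.25 with Section 1.25.1 and Study Management on which AEs go to the SMC; and the reference in pausing criterion 3 to Section 1.20.1. Check the pilot sub-protocol for the same SAE wording. Relabelling diary symptoms as solicited AEs would be one way to settle the first, but it is a matter of preference.

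The cost is a wording amendment, matching guidance on the case report form, and possibly a few more SAE forms. Sample size, significance level and power do not change.
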